#### 11.5. Joint Damage Progression

Joint damage progression based on radiographic evaluations (1 image of both the right and left hands and both the right and left feet, for a total of 4 images, van der Heijde modification of the Sharp scoring system using a dual-reader with adjudication paradigm.) will be evaluated at Screening, Week 48 and Extension Week 24 or at the End-of Study Visit (if not obtained at Week 48 or Extension Week 24), or upon use of protocol prohibited medication or study termination, as applicable.

Two types of joint damage are evaluated: erosion and joint space narrowing.

- Erosion: Defects, cystic changes, and surface erosions are counted in the 10 MCP joints, the eight PIP joints, the two IP joints of the thumbs, the right and left first metacarpal bone, the right and left radius and ulnar bones, the right and left trapezium and trapezoid (as one unit; multangular), right and left navicular bones, right and left lunate bones, the 10 metatarsophalangeal (MTP) joints, and the two IP joints of the big toes. The van der Heijde modification for erosion ranges from 0 (Normal) to 5 (Complete collapse).
- Joint space narrowing: JSN(Joint space narrowing)/ankylosis is assessed in the 10 MCP joints, the eight PIP joints, right and left third, fourth and fifth carpometacarpal (CM) joints, right and left multangular-navicular joints, right and left capitate-navicular-lunate joints, right and left radiocarpal joints, the 10 MTP joints and the two IP joints of the big toes. Joint space narrowing score ranges from 0 (Normal) to 4 (Ankylosis)

Hence the maximum erosion score is 160 for hands and wrists and 120 for feet, and the maximum joint space narrowing score is 120 for hands and wrists and 48 for feet. Scores will be produced by at least two independent readers. If the change in score from baseline to the follow-up timepoints differs between the two readers by more than five, an adjudicator (Reader 3) will read the images for the subject. For cases that are not adjudicated, the average of the two reviewers' scores will be considered the final score. In cases that are adjudicated, the average of the adjudicator's score and the score of the reviewer that is closest to the adjudicator will be provided as the final score. In circumstances where the adjudicator's score is equidistant to both reader 1 and reader 2's score, the final score will be the average of reader 1 and the adjudicator's scores. The average score for each joint will be produced if scores of all readers are non-missing, otherwise the average score for each joint will not be produced. In addition, non-missing score will be used in total score summaries.

The total van der Heijde radiographic joint damage score is the sum of the erosion score (hands, wrists and feet) and the joint space narrowing score (hands, wrists and feet), and hence it ranges from 0 to 448. This will be calculated at each visit for each patient. Descriptive statistics for actual value and change from baseline of the total van der Heijde radiographic joint damage score will be presented by treatment group for the efficacy population and efficacy - Extension Study Period subset at baseline and Week 48, Extension Week 24 visit. If it is not possible to calculate the joint score for a single joint then the particular patient's total score will be excluded from the descriptive statistics.

A listing showing the total van der Heijde radiographic joint damage score will be provided by treatment group for the all-randomized population. In addition, a listing will be provided by treatment group for the all-randomized population showing the raw results for each joint.

#### **11.6. Quality of Life (SF-36) Questionnaire**

The SF-36 questionnaire consists of 36 questions regarding the quality of life of the patient. Results for each of the 36 questions will be recorded. The results will be grouped into the following 8 subscales: Physical Functioning (PF), Role Limitations due to Physical Health (RP), Bodily Pain (BP), General Health Perceptions (GH), Vitality (VT), Social Functioning (SF), Role Limitations due to Emotional Problems (RE), and Mental Health (MH). The Vitality subscale is also known as "Fatigue". The 8 subscales will also be used to derive 2 component summary measures: Physical Component Score (PCS) and Mental Component Score (MCS) [7]. The scores and scales of the SF-36 survey ranges from 0 (worst) to 100 (best), with a higher score indicating a better health-related quality of life.

██████████ will be used in order to derive summary scores for the SF-36 data prior to analysis. The ██████████ will be used to present results. Scoring is standardized using the means and standard ██████████. On this scale, the general population has a mean of 50 and a standard deviation of 10. SF-36 subscale results and component summary measures will be displayed to two decimal places.

Descriptive statistics for actual value and change from baseline will be presented for each of the 8 subscales and 2 summary component scores, by treatment group for the efficacy population, efficacy - 2nd treatment course in Main Study Period subset and efficacy - Extension Study Period subset at baseline, Week 24, Week 48 and Extension Week 24.

A listing will present the raw scores for each of the 36 questions for each patient, by treatment group and visit. In addition, a listing will be presented showing the results of the derived subscales and summary component measures for each patient, by treatment group and visit. Both listings will be based on the all-randomized population.

## **12. Pharmacodynamics**

Analysis of the PD parameters will be conducted using the PD population. The CRP, ESR, anti-CCP, rheumatoid factor (RF), and B-cell counts will be recorded as numeric pharmacodynamic parameters. Any numeric values recorded below the lower limit or above the upper limit of quantification will be set to the respective limit for all subsequent analyses, summaries and plots. In the case where a duplicate measurement of CRP, ESR, anti-CCP or RF is recorded within the same visit, the highest value will be used for analysis as a conservative approach. In case B-cell repeating criteria is applied, that if the variance between repeat results and first run is higher than 10% then repeat result will be used for analysis. Otherwise, first result will be used. All PD information will be listed by treatment group using the PD population.

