dendritic cell function may remain impaired beyond the recovery of B-cells following B-cell depletion (Toubi et al 2007; Youinou et al 2007). Cellular interactions, such as antigen processing and presentation, occur upstream of the proinflammatory cytokine response involving tumor necrosis factor (TNF)-alpha (TNF- α), interleukin-1 (IL-1), and interleukin-6. In addition, production of immunoglobulin M (IgM)-RF and IgG-RF by plasma cells in the rheumatoid synovium may act as a self-perpetuating stimulus for local B-cell proliferation and differentiation (Edwards 1999). Therefore, it appears increasingly evident that B-cells play a key pathogenetic role in the induction and maintenance of RA.

Clinical relevance of depleting B-cells in RA has been demonstrated by using a cytotoxic, chimeric anti-CD20 monoclonal antibody (Rituxan and MabThera) and these products have been approved for the treatment of patients with RA who have an inadequate response to TNF- α blocking agents. Also, previous studies on anti-TNF- α naïve patients with RA who did not benefit from methotrexate (MTX) therapy show that two-thirds of these patients obtained a clinical response following anti-CD20 therapy as measured by the American College of Rheumatology (ACR) 20% improvement criteria (ACR20) (Emery et al 2006). However, the adverse event (AE) profile included a high frequency of infusion-related events requiring premedication with intravenous (IV) steroids. One hypothesis is that rapid B-cell lysis is the driver for the observed in up to 25% of patients treated with a chimeric anti-CD20 antibody (Higashida et al 2005).

Following initial treatment, patients typically remain B-cell depleted for between 6 and 12 months, and some patients show no B-cell recovery for longer periods (MabThera 2015; Rituxan 2014). Currently, retreatment is given upon disease relapse, indicating that patients do not keep their initial clinical benefit over time. Also, in patients who initially do not respond to treatment, the prolonged B-cell depletion presents a risk without clinical benefit.

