### **12.2. ANCOVA of Pharmacodynamic parameters**

ANCOVA will be performed for the PD population at Week 24 where PD blood samples are scheduled for the PD parameters CRP, ESR, anti-CCP and RF. This will be conducted with result as the response, treatment group as fixed effect and baseline values, country, race, study part, interaction of treatment group with study part, gender, prior anti-TNF-  $\alpha$  blocker status

(intolerance case versus inadequate response), and RF or anti-CCP status (both positive versus both negative versus either RF or anti-CCP negative) fitted as covariates. Clinically relevant variables at baseline are used as the covariates for adjusted means. If country is found to be unsuitable as a covariate due to the number of levels, then this may be pooled into the region (EU vs. non-EU). The geometric least squares mean will be calculated by back transforming the least square means, the ratio of geometric least squares means, 95% CI of the ratio and p-value with an interaction effect between study part and treatment group will be produced.

B-cell AUC will be calculated using the linear trapezoidal rule and it will be time normalized by number of minutes since baseline. If the time of sample is missing then the time will be assumed to be 09:00am on the day of sample. If both date and time are missing then the AUC will not be calculated for that patient.

Actual B-cell sampling times will be used for AUC calculation. Patients with missing both post-baseline B-cell counts on the day of the first infusion (15 minutes after end of infusion and 60 ± 15 minutes after end of infusion) will be excluded from the AUC analysis. Patients with a baseline result which is missing or below LLoQ (20cells/mcL) will also be excluded from B-cell AUC analysis.

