The additional ANCOVA will be performed for the B-cell AUC and B-cell counts data up to Week 24 on patients who received first course of study drug. These will include treatment group as a fixed effect, and baseline B-cell count, country (or region), gender, race, study part, interaction of treatment group with study part, prior anti-TNF- $\gamma$  blocker (intolerance case versus inadequate response), and RF or anti-CCP status (both positive versus both negative versus either RF or anti-CCP negative) fitted as covariates. The geometric least squares mean will be calculated by back transforming the least square means. The ratio of geometric least squares means, 95% CI (geometric least squares mean and ratio) and p-value with an interaction effect between study part and treatment group will be produced. Additional ANCOVA for the B-cell AUC and the B-cell counts will be conducted in patients whose ADA status result at Week 24 is “Negative”.

All pharmacodynamic analyses will be conducted using two treatment groups, CT-P10 and reference products group on Part 2.

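### At visits where most B-cell counts fall below 20 cells/mcL, replacing them by 20 pulls the ANCOVA ratio towards 1 and makes its 95% CI too narrow

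*SAP*

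**What the plan says.** - SAP section 12 applies one rule to all numeric PD parameters, B-cell counts included: a value below the lower or above the upper quantification limit "will be set to the respective limit for all subsequent analyses, summaries and plots".
- SAP section 12.2 gives the B-cell limit in passing: "Patients with a baseline result which is missing or below LLoQ (20cells/mcL) will also be excluded from B-cell AUC analysis". That exclusion concerns baseline only and the AUC only. A post-dose count below 20 stays in, as 20.
- The same section continues: "The additional ANCOVA will be performed for the B-cell AUC and B-cell counts data up to Week 24". The output is "The ratio of geometric least squares means, 95% CI (geometric least squares mean and ratio) and p-value with an interaction effect", and the comparison is CT-P10 against the pooled reference group.
- Protocol section 1 (Introduction) says that after initial treatment "patients typically remain B-cell depleted for between 6 and 12 months". Protocol section 7.3 names B-cell kinetics, with depletion and recovery, as a secondary PD endpoint.
- SAP section 12 has no method for censored data, no table of B-cell values below the limit, and no analysis of time to depletion or recovery. SAP section 10.1, on PK, does treat the problem: a mean below the limit is shown as such, and its SD and CV are not reported. Section 12 has no counterpart.

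**The concern.** B-cell depletion is the pharmacodynamic effect most directly tied to how rituximab acts, so in a biosimilar trial this is the PD comparison that readers will look at first. A value known only to lie below 20 is entered as though it were measured as exactly 20.

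If most patients in both groups are in that state, two things follow. The log means of both groups move towards ln 20, so their ratio moves towards 1. The residual SD also collapses, because most of the sample is one constant, and the interval narrows with it. The result can then be read as precise agreement when what it shows is mainly that the assay could not tell the counts apart. B-cell AUC inherits the same floor over the depleted part of the curve; I have not quantified that.

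**Working it through.** **Inputs.** Limit of 20 cells/mcL and the substitution rule: SAP sections 12 and 12.2. Group sizes of 133 and 189: SAP section 5.2, the evaluable numbers for DAS28, used here as a stand-in for the PD population. The documents give no SD, margin, power or expected ratio for the B-cell ANCOVA, so there is no stated figure to reproduce. (The DAS28 power behind those group sizes does reproduce: SE = 1.32 × √(1/133 + 1/189) = 0.149; 2Φ(0.5/0.149 − 1.645) − 1 ≈ 91%, against about 90% stated.)

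**Assumptions.** Log-normal counts at a single visit; log-SD 1.0, then 1.5; share of the reference group below 20 from 50% to 99%; no covariates.

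**Exact case.** If every count in both groups is below 20, the ratio is 20/20 = 1 with zero residual variance, even for true means of 2 against 10.

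**General formula.** Let p be the reference share below 20 and a = z_p. With log-SD 1, substitution places the group log mean above ln 20 by

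e(a) = φ(a) − a[1 − Φ(a)],

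with variance (1 + a²)[1 − Φ(a)] − aφ(a) − e(a)². For a true ratio R, CT-P10 has a − ln R in place of a.

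**Worked case: p = 90%, R = 2.**
- Reference: a = 1.2816; e = 0.1755 − 1.2816 × 0.1000 = 0.0473; variance 0.037.
- CT-P10: a = 1.2816 − 0.6931 = 0.5884; e = 0.3355 − 0.5884 × 0.2781 = 0.1719; variance 0.147.
- Reported ratio: exp(0.1719 − 0.0473) = 1.13.
- Pooled SD: √[(132 × 0.147 + 188 × 0.037)/320] = 0.287, against a true 1.0.
- SE: 0.287 × 0.1132 = 0.0325. The 95% CI is about 1.06 to 1.21, an upper/lower ratio of 1.14. Fully observed data would give exp(2 × 1.967 × 0.1132) = 1.56.

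**Simulation** (4,000 trials per cell, log-SD 1.0; the reported ratios agree with the formula):

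| Reference below 20 | Reported, true ratio 2 | CI upper/lower | CI covers 2 | Reported, true ratio 3 | Reported, true ratio 0.5 |
|---|---|---|---|---|---|
| 50% | 1.55 | 1.35 | 11% | 2.16 | 0.78 |
| 80% | 1.24 | 1.20 | 0% | 1.54 | 0.92 |
| 90% | 1.13 | 1.14 | 0% | 1.31 | 0.96 |
| 95% | 1.07 | 1.09 | 0% | 1.18 | 0.98 |
| 99% | 1.02 | 1.04 | 0% | 1.05 | 1.00 |

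With log-SD 1.5 and a true ratio of 2, the reported values are 1.21, 1.11, 1.06 and 1.01 at 80%, 90%, 95% and 99% below, again with 0% coverage.

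**Limits of the effect.** For a true ratio of 3 at log-SD 1.0 and 80% to 99% below, the CI excludes 1 in at least 95% of trials. At log-SD 1.5 and 99% below, that falls to 57%. When the true ratio is 1, coverage stays near 95% in almost every setting.

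**Alternatives on the same data.**
- *Proportion below 20.* In the worked case the shares are 90.0% and 72.2%, a difference of 17.8 points. SE = √(0.722 × 0.278/133 + 0.9 × 0.1/189) = 0.045, so the 95% CI is about 9 to 27 points.
- *Left-censored (Tobit) regression, log-SD 1.0, no covariates, 300 trials.* A true ratio of 2 is estimated as 1.98 at 90% below (coverage 95%, upper/lower 1.97) and 2.00 at 95% below (coverage 92%, upper/lower 2.34).
- *Where Tobit fails.* With a reference geometric mean of 1 and CV 100%, log-SD = √ln 2 = 0.833. P(count > 20) is 0.00016 there and 0.0028 at a mean of 2. That is 189 × 0.00016 = 0.03 and 133 × 0.0028 = 0.4 patients above the limit, which is too few to fit any ratio.

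**The case against.** The strongest counter-argument is that the decisive number is missing. The protocol says depleted; it does not say below 20 cells/mcL, and no section gives the share of post-dose counts under the limit. The count data up to Week 24 also include first-infusion-day samples and any early recovery, where counts may be quantifiable. This stands: the size of the effect is conditional on an assumed share.

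Second, a difference between, say, 1 and 2 cells/mcL cannot be seen by this assay, so failing to cover that ratio is failing at something the data cannot supply without a distributional assumption. This also stands, and it argues for comparing proportions below the limit. It does not argue for printing a ratio whose CI implies more knowledge than the data hold.

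Third, the floor would be partly visible. SAP section 12.1 tabulates minimum, median and SD by time point, and section 12.3 plots medians and lists individual counts. A median of 20 with a small SD would alert a careful reader. This softens the harm but leaves the interval as it is.

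Fourth, B-cell kinetics is a secondary endpoint with no margin or pass rule; the similarity conclusions rest on PK and DAS28. This stands and limits the severity.

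**Conclusion.** The point holds conditionally. At time points where most counts are below 20, the planned ratio is pulled towards 1 and its 95% CI is not an interval for the ratio of B-cell counts. With 80% to 99% of the reference group below 20, a true ratio of 2 is reported as 1.24 down to 1.02 at log-SD 1.0. This rests on assumed log-normal counts, DAS28 group sizes and no covariates. The direction does not depend on those choices; the size does.

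A reader might infer more: that the analysis would show near-perfect similarity whatever the true difference. The documents do not support that. It is exact only if both groups lie wholly below 20. Otherwise a large difference still appears, reduced in size, and the CI often excludes 1: a true ratio of 3 at 90% below is reported as about 1.31, CI about 1.20 to 1.42. Nor may one infer that a formal similarity claim depends on it, since none is attached to this endpoint. The risk is a misleading size and precision in a supporting result. It should be corrected, but it does not threaten the primary conclusions.

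**What to change.** In SAP section 12.2:

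1. At each post-dose visit, report n (%) of patients with B-cell counts below the limit by group, with a 95% CI for the difference, and make this the main comparison of depletion.
2. Restrict the ANCOVA of B-cell counts to time points where most values are quantifiable, and state the threshold before unblinding.
3. Where enough values exceed the limit to fit it, add a left-censored (Tobit) regression as a supportive analysis, with the section 12.2 covariates as far as the data allow. Do not rely on it where nearly all values are censored.

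The cost is SAP wording and one extra table from data already collected. The only loss is that fully depleted visits will have no geometric mean ratio; at those visits the data cannot supply one.

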### **12.1. Descriptive Statistics of Pharmacodynamic parameters**

Descriptive statistics will be provided for the CRP, ESR, anti-CCP and RF parameters (actual value and change from baseline) for the pharmacodynamic population, pharmacodynamic – opnd treatment course in Main Study Period subset and pharmacodynamic – Extension Study Period subset by treatment group and visit. Descriptive statistics will consist of n, mean, SD, geometric mean, CV, minimum, median and maximum. The number and percentage of patients within each category will be displayed for baseline and for each post-baseline visit by treatment group.

The number and percentage of patients within each category of the anti-CCP (Negative, Positive, or Missing) and RF (Negative, Positive or Missing) parameter will be displayed in shift tables for the pharmacodynamic population at Week 24, for pharmacodynamic – 2nd treatment course in Main Study Period subset at Week 24 and Week 48, and for the pharmacodynamic – Extension Study Period subset at Extension Week 0 and Extension Week 24 by treatment group. Anti-CCP results equal to or greater than 17 U/ml will be considered as “positive” while those less than 17 U/ml will be considered as “negative”. RF results greater than 10 IU/ml will be considered as “positive” while those equal to or less than 10 IU/ml will be considered as “negative”.

The descriptive statistics (actual value and change from baseline) will also be summarized for B-cell counts for the pharmacodynamic population, pharmacodynamic – 2nd treatment course in Main Study Period subset and pharmacodynamic – Extension Study Period subset by treatment group and time-point up to Extension Week 24, including the records at pre-dose, end of study drug infusion, and 1 hour after the end of study drug infusion. For patients from Part 1, additional sample will be collected after 24 hours from the end of study drug infusion. The descriptive statistics will consist of n, mean, SD, geometric mean, CV, minimum, median and maximum.

### **12.2. ANCOVA of Pharmacodynamic parameters**

ANCOVA will be performed for the PD population at Week 24 where PD blood samples are scheduled for the PD parameters CRP, ESR, anti-CCP and RF. This will be conducted with result as the response, treatment group as fixed effect and baseline values, country, race, study part, interaction of treatment group with study part, gender, prior anti-TNF-  $\alpha$  blocker status

(intolerance case versus inadequate response), and RF or anti-CCP status (both positive versus both negative versus either RF or anti-CCP negative) fitted as covariates. Clinically relevant variables at baseline are used as the covariates for adjusted means. If country is found to be unsuitable as a covariate due to the number of levels, then this may be pooled into the region (EU vs. non-EU). The geometric least squares mean will be calculated by back transforming the least square means, the ratio of geometric least squares means, 95% CI of the ratio and p-value with an interaction effect between study part and treatment group will be produced.

B-cell AUC will be calculated using the linear trapezoidal rule and it will be time normalized by number of minutes since baseline. If the time of sample is missing then the time will be assumed to be 09:00am on the day of sample. If both date and time are missing then the AUC will not be calculated for that patient.

Actual B-cell sampling times will be used for AUC calculation. Patients with missing both post-baseline B-cell counts on the day of the first infusion (15 minutes after end of infusion and 60 ± 15 minutes after end of infusion) will be excluded from the AUC analysis. Patients with a baseline result which is missing or below LLoQ (20cells/mcL) will also be excluded from B-cell AUC analysis.

The additional ANCOVA will be performed for the B-cell AUC and B-cell counts data up to Week 24 on patients who received first course of study drug. These will include treatment group as a fixed effect, and baseline B-cell count, country (or region), gender, race, study part, interaction of treatment group with study part, prior anti-TNF- $\gamma$  blocker (intolerance case versus inadequate response), and RF or anti-CCP status (both positive versus both negative versus either RF or anti-CCP negative) fitted as covariates. The geometric least squares mean will be calculated by back transforming the least square means. The ratio of geometric least squares means, 95% CI (geometric least squares mean and ratio) and p-value with an interaction effect between study part and treatment group will be produced. Additional ANCOVA for the B-cell AUC and the B-cell counts will be conducted in patients whose ADA status result at Week 24 is “Negative”.

All pharmacodynamic analyses will be conducted using two treatment groups, CT-P10 and reference products group on Part 2.

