2.2 Secondary Objectives

2.2.1 Secondary Objectives: Part 1

The secondary objectives of Part 1 of the study are:

- To assess the additional PK variables of CT-P10, Rituxan and MabThera during the first course of treatment (over the first 24 weeks).
- To evaluate the pharmacodynamics and safety of CT-P10, Rituxan and MabThera (over the first 24 weeks).

2.2.2 Secondary Objective: Part 2

The secondary objective of Part 2 of the study is:

• To evaluate the additional pharmacokinetics (up to Week 48), efficacy, pharmacodynamics, overall safety, and biomarkers of CT-P10 compared with reference products.

3 Investigational Plan

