7.8.3 Pharmacodynamic Analyses

All PD data will be listed and summarized by treatment, where appropriate. The comparison of the concentration of B-cell kinetics between CT-P10, Rituxan and MabThera will be performed using ANCOVA, with treatment as a fixed effect and baseline values, country, gender, race, prior anti-TNF- α blocker status(inadequate response versus intolerant case), and RF or anti-CCP status (both positive versus both negative versus either RF or anti-CCP negative) fitted as covariates. If country is found to be unsuitable as a covariate due to the number of levels, then this may be pooled into a new variable, region defined in SAP, for use as a covariate. Point estimates and 95% CIs will be provided. Pharmacodynamic data will also be summarized using quantitative descriptive statistics (including geometric mean and CV, where appropriate).

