**Table 1: Populations and Subsets of Analysis**

Populations	Subsets
Main Study Period: Part 1	
all-randomized	
safety	
pharmacokinetic	pharmacokinetic (antibody negative subset) pharmacokinetic (antibody positive subset)
Main Study Period: Part 2	
all-randomized	all-randomized (antibody negative subset)
safety	safety – 2 nd treatment course in Main Study Period subset
efficacy	efficacy (antibody negative subset) efficacy (antibody positive subset) efficacy – 2 nd treatment course in Main Study Period subset
pharmacokinetic	pharmacokinetic (antibody negative subset) pharmacokinetic (antibody positive subset) pharmacokinetic – 2 nd treatment course in Main Study Period subset
pharmacodynamic	pharmacodynamic (antibody negative subset) pharmacodynamic – 2 nd treatment course in Main Study Period subset
Extension Study Period	
all-randomized	all-randomized – Extension Study Period subset
safety	safety – Extension Study Period subset
efficacy	efficacy – Extension Study Period subset
pharmacodynamic	pharmacodynamic – Extension Study Period subset

All-randomized, safety and PK populations and its subsets will be defined for the patients from Part 1 and 2, respectively. Efficacy and PD population and its subsets will be defined for the Part 2. Population for Part 2 will include patients from Part 1.

Patients who have any major protocol deviations (as defined in [Section 5.6](#)) may be excluded only from the population (PD and/or Efficacy) that would be affected by the deviation. Patients from the significant GCP non-compliance sites as defined in [Section 5.6](#) will be excluded in all populations.

The number of patients in all populations will be tabulated by the treatment group in each relevant Part and study period. A listing will also be produced, displaying this data.

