### **5.7. Display of Data by Treatment**

All analysis result of Main Study Period excluding ANCOVA will be displayed by the following groups: CT-P10, Rituxan, MabThera, and combined Rituxan and MabThera group.

Analysis of the general and PK section in Main Study Period will be conducted in Part 1 and 2 separately.

All analysis result of Extension Study Period will be displayed by the following groups: CT-P10 maintenance (Group 1), Switched from Rituxan (Group 2), Rituxan maintenance (Group 3), Switched from MabThera (Group 4), and combined Switched from Rituxan and Switched from MabThera group.

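### The SAP replaces the protocol's three-product B-cell ANCOVA with CT-P10 versus pooled reference, defines no Part 1 PD population, and does not record the change, so the Part 1 PD objective is only partly answered

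*SAP*

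**What the plan says.** **Protocol.** The Part 1 secondary objective (2.2.1) reads "To evaluate the pharmacodynamics and safety of CT-P10, Rituxan and MabThera (over the first 24 weeks". Section 7.8.3 states: "The comparison of the concentration of B-cell kinetics between CT-P10, Rituxan and MabThera will be performed using ANCOVA", with point estimates and 95% CIs. Section 7.8 lists three product pairs for the Part 1 analyses, pools the two references for the Part 2 analyses up to Week 48, and requires the SAP to record any departure from the planned analyses.

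**SAP.** Section 3.1.2 repeats the Part 1 objective. The text under Table 1 (5.4) then says "Efficacy and PD population and its subsets will be defined for the Part 2" and "Population for Part 2 will include patients from Part 1". Table 1 itself gives Part 1 all-randomized, safety and PK populations only. Section 12.2 fits ANCOVAs to CRP, ESR, anti-CCP, RF, B-cell AUC and B-cell counts, with study part and a treatment-by-part interaction in the model, and closes with "All pharmacodynamic analyses will be conducted using two treatment groups, CT-P10 and reference products group on Part 2". Outside ANCOVA, section 5.7 provides: "All analysis result of Main Study Period excluding ANCOVA will be displayed by the following groups: CT-P10, Rituxan, MabThera, and combined Rituxan and MabThera group". The only split by part that it makes is this: "Analysis of the general and PK section in Main Study Period will be conducted in Part 1 and 2 separately". PD is not among the sections split.

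**The concern.** Part 1 is the only place where all three products are randomised against each other (1:1:1), and only Part 1 patients give the extra 24-hour B-cell sample. The protocol names the three products in its B-cell ANCOVA. The SAP reduces this to a single contrast of CT-P10 with a mixture of Rituxan and MabThera, and nothing in the SAP marks it as a change.

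What is at stake is product-level inference on B-cell response. As planned, the trial gives no estimate with a CI for CT-P10 versus Rituxan, CT-P10 versus MabThera or Rituxan versus MabThera on any PD measure, although the data are collected. A difference confined to MabThera would reach the pooled contrast only in weakened form.

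**Working it through.** **1. Group sizes.** Part 1 allocates 189 patients 1:1:1, so 63 per arm. The later 172 patients are allocated 1:1 to CT-P10 and Rituxan, so 86 per arm (SAP 5.2, Protocol synopsis).
- CT-P10: 63 + 86 = 149
- Rituxan: 63 + 86 = 149
- MabThera: 63
- Reference: 149 + 63 = 212

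These reproduce the plan's 149 and 212.

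**2. Protocol and SAP side by side.**

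| Item | Protocol | SAP |
|---|---|---|
| B-cell ANCOVA groups | CT-P10, Rituxan, MabThera (7.8.3) | CT-P10, pooled reference (12.2) |
| Contrasts for Part 1 | three pairs (7.8, general list) | none for PD |
| PD population for Part 1 | not separated by part (7.6) | none; Part 2 only, including Part 1 patients (5.4) |
| Departure recorded | required (7.8) | no |

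**3. What product-level PD output remains in the SAP.**
- Section 12.1 with 5.7: descriptive statistics by product for B-cell counts, CRP, ESR, RF and anti-CCP. In these tables 63/149 = 42% of the CT-P10 and Rituxan columns comes from Part 1, while the MabThera column is entirely Part 1. The randomised 63/63/63 comparison is not shown on its own.
- B-cell AUC: analysed in the two-group ANCOVA (12.2) and listed by patient (12.3). There is no summary by product.
- Plots of B-cell counts, CRP and ESR (12.3): two groups.

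**4. MabThera's weight in the pooled reference.**
- By patients: 63/212 = 0.297.
- If the least squares means weight the two parts equally, MabThera is half the reference in Part 1 and absent among later patients: (0.5 + 0)/2 = 0.25.

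**5. Dilution, as an illustration.** The documents give no expected product difference, so the true ratios below are assumptions. Let Rituxan equal CT-P10 and let MabThera differ by a true ratio r. On the log scale the pooled ratio is r^w.

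| Assumed r | w = 0.297 | w = 0.25 |
|---|---|---|
| 1.10 | 1.029 | 1.024 |
| 1.25 | 1.069 | 1.057 |
| 1.50 | 1.128 | 1.107 |

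**6. Interaction term.** With r = 1.25, the reference/CT-P10 ratio is 1.25^0.5 = 1.118 among Part 1 patients and 1.00 among later ones. The interaction can respond to that gap. Within Part 1, however, the reference level still combines Rituxan and MabThera, so the term cannot say which product differs. It would also respond to any other reason for a treatment effect to vary between parts.

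**7. Precision of the missing contrasts.** No B-cell SD is given, so standard errors are stated as multiples of SD, at planned sizes and before covariate adjustment.
- Part 1 pair: sqrt(1/63 + 1/63) = 0.178 × SD
- Pooled contrast: sqrt(1/149 + 1/212) = 0.107 × SD
- Ratio: 0.178/0.107 = 1.67

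**The case against.** The case for leaving the SAP alone has real content.

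- **The objective says evaluate.** The Part 1 PK objective (protocol synopsis and SAP 3.1.1) says evaluate and compare; the PD objective says only evaluate. A reader might infer that an objective of comparing PD goes unmet, or that PD by product is not reported at all. Neither is supported: the verb differs, and SAP 5.7 with 12.1 keeps descriptive tables by product. The three-product ANCOVA in Protocol 7.8.3 is nonetheless an explicit comparison and does not depend on that verb.
- **Pooling is itself planned.** The protocol combines the references for Part 2, and the Part 2 objective covers PD against reference products. The pooled ANCOVA serves that objective and should stay. It does not replace the three-product one.
- **Three pairwise PD contrasts are not spelled out.** Protocol 7.8.3 names three products but neither pairs, Part 1 nor B-cell AUC. The pairs come from the general Part 1 list in 7.8. Counting three promised PD contrasts as missing is therefore a joint reading of two sections.
- **The interaction term is a check.** It is a partial one, for the reason in step 6 of the working.
- **The gain is unproven.** No PD margin, SD or power is stated, and values below quantification are set to the limit (SAP 12), which may compress differences during depletion. This stands, but it applies equally to the pooled ANCOVA that the SAP does run.
- **The SAP may change the analysis.** It may, if it says so. A recorded and justified departure would satisfy Protocol 7.8, though it would still give no product-level estimates.

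**Conclusion.** The point holds in this form: an analysis named in the protocol has been replaced without being recorded, and the Part 1 PD objective is only partly answered. What is missing is a Part 1 PD population, a Part 1-only PD summary, a summary of B-cell AUC by product, and any product-level contrast with a CI.

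The pooled contrast cannot stand in for these. With MabThera at 25-30% of the reference, assumed true ratios of 1.10, 1.25 and 1.50 would appear as about 1.02-1.03, 1.06-1.07 and 1.11-1.13. That range rests on planned group sizes, on Rituxan being equal to CT-P10, and on ratios chosen for illustration. It does not suggest that a difference exists.

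The closing sentence of SAP 12.2, read literally, also conflicts with SAP 5.7, because it would remove the product-level tables. Read as governing the ANCOVAs of its own section, it does not. The wording should settle which is meant.

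The primary PK and efficacy conclusions are unaffected. The change is still worth making, because it restores a planned analysis from data already collected.

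**What to change.** 1. In SAP 5.4 and Table 1, define a PD population for Part 1.
2. In SAP 12.2, add for Part 1 patients the protocol's ANCOVA of B-cell AUC and B-cell counts up to Week 24, with three treatment levels and without the study-part and interaction terms. Report the three pairwise geometric mean ratios with 95% CIs, labelled as descriptive secondary results.
3. Keep the pooled Part 2 ANCOVA as it is.
4. Limit the closing sentence of SAP 12.2 to the Part 2 ANCOVAs, so that it agrees with SAP 5.7.

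The cost is SAP wording and a few extra tables, with no new patients or samples. With about 63 per arm the Part 1 intervals will be roughly 1.67 times as wide as the pooled one at the same SD. That is acceptable because no PD margin or power is claimed.
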